### 15.2.2 Vital signs

Vital signs comprise systolic and diastolic blood pressure, pulse rate, respiratory rate, body weight, and BMI. Vital signs will be measured at each visit (Visit 1 to Visit 11). At Visit 2 through Visit 5, vital signs will be taken once at least 15 minutes before the infusion and once at least 15 minutes after the infusion. Body weight will be included as a vital sign and will be measured at all visits (only once at Visit 2 through Visit 5, prior to the infusion). BMI will be derived.

Vital signs parameters will be analyzed as described in Section 15.2 with individual specifications outlined in Table 4.

Table 4: Analysis of vital signs parameters

	Parameter	Table of descriptive statistics	Frequency table (low/high)	Shift table	Mean plot	Shift plot
Vital signs parameters (continuous)	Blood pressure (diastolic)	X	X	X		
	Blood pressure (systolic)	X	X	X		
	BMI a	X	X	X		
	Body weight	X	X	X		
	Pulse rate	X	X	X		
	Respiratory rate	X	X	X		

a) BMI will be derived.  
BMI = body mass index.

### 15.2.3 Electrocardiogram

Twelve-lead ECGs will be recorded from Visit 1 to Visit 6, at Visit 9, and at Visit 11. At Visit 2 through Visit 5, triplicate ECGs will be recorded once at least 15 minutes before the infusion and once at least 15 minutes after the infusion. One triplicate ECG will be recorded at all other visits.

Electrocardiogram parameters will include heart rate and the following ECG intervals: QRS, PR, RR, QT, QTcB, and QTcF. Twelve-lead ECGs are recorded in triplicate. For the analysis, the mean of the 3 individual values will be calculated for each parameter.

Electrocardiogram (ECG) parameters (continuous) will be analyzed as described in Section 15.2 with individual specifications outlined in Table 5.

Table 5: Analysis of ECG parameters

	Parameter	Table of descriptive statistics	Frequency table (low/high)	Shift table	Mean plot	Shift plot
ECG parameters (continuous)	Heart rate	X	X	X		
	PR interval	X	X	X		
	QRS interval	X	X	X		
	QT interval	X	X	X		
	QTcB interval	X	X	X		
	QTcF interval	X	X	X		
	RR interval	X	X	X		

ECG = electrocardiogram; QTcB = Corrected QT interval (according to Bazett's formula); QTcF = Corrected QT interval (according to Fridericia's formula).

The ECG printouts will be interpreted by the investigator as “normal”, “abnormal, but clinically not relevant”, or “abnormal and clinically relevant”. Results from this interpretation will be reported in subject data listings. Moreover, the results from the ECG interpretation will be descriptively summarized.

In addition, a subject data listing of all abnormal, clinically relevant findings as documented by the investigator in the eCRF will be created.

### 15.3 Physical examination

Physical examination outcomes will be recorded at Visit 1, before the IMP infusion at Visit 2, and from Visit 8 through Visit 11 in the follow-up period. A general physical examination will be done at the Enrollment Visit (Visit 1) by rating each body system as *normal* or *abnormal*. At all subsequent visits, including unscheduled visits, updates of the physical status since the previous visit is recorded by rating each body system as *unchanged* or *changed*.

All physical examination results will be presented in a subject data listing.

### 15.4 Bone biopsy procedures

Data collected in the eCRF regarding bone biopsy procedures and tetracycline intake will be listed for all subjects in the Bone Biopsy Set. No further statistical analysis is planned in this SAP. Bone biopsy data will be analyzed and reported separately by a dedicated bone biopsy service provider.

### 15.5 Primary endpoint

The primary endpoint of this trial is a binary safety endpoint assessing whether or not a subject experienced any TEAE. The incidence and incidence rate for any TEAE is included in the summary of the number and percentage of subjects with TEAE (Section 15.1).

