## 1.5 Statistical analyses

As this is a single-arm trial, no treatment comparisons will be conducted, but development from baseline over time will be investigated. All analyses in this trial will be of exploratory nature. No statistical testing of inference is planned in this trial. There will be no multiplicity adjustment for any of the analyses. All confidence intervals used to describe the data will be determined using a 95% confidence level.

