### 1.5.1 Sample size rationale

The sample size is intended to maximize available safety data in line with the FDA regulatory requirements to support product registration. It is estimated that approximately 290 subjects will be included in this trial.

If the expected number of bone biopsies or bone densitometry and MRI assessments are not obtained, it is not planned to increase the number of subjects included in the trial.

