#### **14.1.6.1.1 Analysis of the primary endpoint**

The primary endpoint of this trial is a binary endpoint assessing whether or not a subject experienced any TEAE.

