### 5.2 Sample size

The sample size is intended to maximize available safety data to support product registration. In combination with subjects receiving active treatment in the ongoing placebo-controlled trial (KF7013-01) and further planned trials of neridronic acid, the number of subjects included in this trial is intended to support regulatory requirements for at least 500 subjects on neridronic acid evaluated for safety. It is estimated that approximately 290 subjects will be included in this trial.

For bone biopsies, results from 15 evaluable biopsy specimens are considered adequate to be able to identify qualitative bone abnormalities such as osteomalacia as well as quantitative indicators of impaired mineralization.

For bone densitometry and magnetic resonance imaging (MRI) assessments, results from 30 subjects are considered sufficient to demonstrate feasibility and support a rationale for the future use of these assessments in trials of neridronic acid in CRPS.

If the expected number of bone biopsies or bone densitometry and MRI assessments are not obtained, it is not planned to increase the number of subjects included in the trial.

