## 15.6 Secondary safety endpoint

The secondary safety endpoint is the occurrence of permanent discontinuation from treatment due to an adverse event. The number and percentage of subjects permanently discontinued from treatment is included in the summary of discontinuations from IMP (Section 10.2).

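### The SAP pre-specifies no confidence interval for the two safety proportions, and takes the secondary one from a table with the wrong denominator

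*SAP*

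**What the plan says.** Protocol 14.1.6.1.1 defines the primary endpoint: "The primary endpoint of this trial is a binary endpoint assessing whether or not a subject experienced any TEAE". SAP 15.5 sets out its analysis in one sentence: "The incidence and incidence rate for any TEAE is included in the summary of the number and percentage of subjects with TEAE", referring to the overview table in SAP 15.1. SAP 15.6 states that "The secondary safety endpoint is the occurrence of permanent discontinuation from treatment due to an adverse event", asks for a number and percentage, and sends the reader to the IMP discontinuation summary in Section 10.2.

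Three general rules bear on this:

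- Protocol 1.5 says "No statistical testing of inference is planned in this trial" and "All confidence intervals used to describe the data will be determined using a 95% confidence level". The second sentence sets the level of any interval that is used. It does not assign one to these endpoints.
- SAP 8.1 gives categorical variables counts and percentages only. Time-to-event variables get 95% intervals for the quartiles, with log-log bounds for the survival estimate.
- SAP Table 1 assigns both safety endpoints to the Safety Set. In SAP 10.2 the population is the allocated subjects, and the percentages attached to discontinuation reasons use the subjects who discontinued as denominator.

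On size, Protocol 1.5.1 says "It is estimated that approximately 290 subjects will be included in this trial".

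**The concern.** With no comparator and no test, an estimate with stated precision is the most these endpoints can offer. The trial exists to supply safety data: "The sample size is intended to maximize available safety data in line with the FDA regulatory requirements to support product registration". A bare percentage does not show how far the true rate could lie from it. That matters most for the low-count rows of the SAP 15.1 overview, such as IMP discontinuation, serious related TEAEs and deaths.

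The second problem concerns the figure itself. The secondary endpoint asks what share of treated subjects permanently stopped IMP because of an adverse event. A table whose percentages are shares of the discontinuers answers a different question: of those who stopped, how many stopped for this reason. If the 15.6 cross-reference is followed literally, the report would show the wrong proportion for a named endpoint, with or without an interval.

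**Working it through.** **Inputs.** N is about 290 (Protocol 1.5.1), confidence level 95% (Protocol 1.5). The documents give no expected event rates, so all rates below are assumptions shown over a range. The planned 290 rests on regulatory exposure and has no power or precision calculation behind it, so there is no figure to reproduce.

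**1. Exact (Clopper-Pearson) interval for x/n.** Lower limit = 2.5% quantile of Beta(x, n − x + 1). Upper limit = 97.5% quantile of Beta(x + 1, n − x). With x = 0 the upper limit is 1 − 0.025^(1/n).

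| Endpoint | x/290 | % | Exact 95% CI (%) |
|---|---|---|---|
| Any TEAE | 145 | 50 | 44.1 to 55.9 |
| Any TEAE | 203 | 70 | 64.4 to 75.2 |
| Any TEAE | 261 | 90 | 86.0 to 93.2 |
| IMP discontinuation due to AE | 0 | 0 | 0 to 1.26 |
| IMP discontinuation due to AE | 3 | 1.0 | 0.21 to 2.99 |
| IMP discontinuation due to AE | 9 | 3.1 | 1.43 to 5.81 |
| IMP discontinuation due to AE | 14 | 4.8 | 2.66 to 7.97 |
| IMP discontinuation due to AE | 15 | 5.2 | 2.92 to 8.39 |

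For any TEAE at 50% to 90%, the half-width runs from 5.9 down to 3.6 points. At zero events, 1 − 0.025^(1/290) = 1.26%. If only 261 subjects (90% of 290) were treated, it would be 1.40%.

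**2. What the Kaplan-Meier analysis covers for any TEAE.** SAP 15.1.1 always summarizes time to onset of TEAE by time-to-event methods, so the interval rules of SAP 8.1 apply. Assume no censoring before the end of the trial. Then S = 1 − p, the standard error of log S is √(p/(nS)), and the log-log limits are S^exp(±1.96·se/|log S|). At p = 0.70: se = √(0.70/(290 × 0.30)) = 0.090, |log 0.30| = 1.204, and the limits for 1 − S are 64.7% to 75.2%. The exact interval is 64.4% to 75.2%. At p = 0.80 the two are 75.2% to 84.4% and 74.9% to 84.5%. Agreement is close under this assumption. With dropout it weakens, because a subject who leaves without a TEAE is censored in one analysis and counted as a non-event in the other.

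**3. What it covers for IMP discontinuation.** SAP 15.1 runs the AE-specific time-to-event analysis only if more than 5% of subjects permanently discontinue IMP due to a TEAE. Since 0.05 × 290 = 14.5, this needs at least 15 subjects. At 14 or fewer there is no planned interval. SAP 10.2 has another conditional analysis, triggered at more than 10%, but it pools all reasons for stopping IMP.

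**4. The denominator.** Suppose 20 subjects stop IMP, 12 of them for an adverse event. Under the 10.2 rule: 12/20 = 60%. In the Safety Set: 12/290 = 4.1%, exact 95% CI 2.2% to 7.1%. The two differ by the factor 290/20 = 14.5. The SAP 15.1 overview already has a row for TEAE leading to discontinuation from IMP, with the number of subjects as denominator.

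**The case against.** The best defense is that the plan is consistent and loses no information. The protocol calls all analyses exploratory and promises no interval for these proportions. SAP 8.1 applies the same rule to every categorical variable: the pain responder rates and the PGIC response are efficacy proportions, and they have no interval either. The 95% intervals elsewhere in the SAP are for means, model estimates or time-to-event summaries. An exact interval depends only on the count and N, and SAP 15.1 reports both for each endpoint.

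Most of this stands, and it rules out three stronger readings that a reader might infer:

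- *That the safety analysis contains no interval at all.* The unconditional Kaplan-Meier analysis of any TEAE has one.
- *That the trial cannot say which event rates it excludes.* Anyone can compute the limits from the reported count and N. What is missing is pre-specification of the interval and its method.
- *That safety is handled less carefully than efficacy.* The dividing line is between proportions and means, not between safety and efficacy.

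A zero or low count is also implausible for any TEAE over 52 weeks, since Protocol 8.2 describes flu-like symptoms as the most common side effect of the class. And SAP 5.2 ties the sample size to a database pooled across trials ("regulatory requirements for at least 500 subjects on neridronic acid evaluated for safety"), so a bound near 1% from this trial alone is not the stated purpose of N.

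The defense does not answer the conditional gap for the secondary endpoint or the 10.2 denominator.

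**Conclusion.** The point holds in a limited form. Neither safety proportion has a pre-specified interval. For any TEAE the practical loss is small, because the Kaplan-Meier bounds come close to the exact ones when few subjects leave early without an event. For permanent IMP discontinuation due to an adverse event the gap is real: no interval is planned at 14/290 or fewer, where the exact upper limit runs from 1.26% (no events) to 7.97% (14 events). The cross-reference to Section 10.2 is the sharper defect, since it can replace a rate of about 4% with a share of 60% in the illustration.

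This rests on assumed event rates, on 290 as an approximate planned number, and on reading the 10.2 denominator as applying to the adverse-event reason row that 15.6 would use. It is a reporting improvement and gives no ground for changing N.

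**What to change.** - In SAP 15.5, 15.6 and the subject-level overview of 15.1, report n/N (%) with the Safety Set as denominator and an exact Clopper-Pearson two-sided 95% interval. State the upper limit also when no event is seen (about 1.3% if N is 290).
- In SAP 15.6, replace the reference to Section 10.2 with the 15.1 row for TEAE leading to discontinuation from IMP, and say that the row means permanent discontinuation. The 10.2 table can stay as a description of reasons among those who stopped.

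The cost is one extra column and one changed cross-reference. No new data are needed, and neither a test nor a multiplicity question arises. The 95% level matches Protocol 1.5.

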## 15.6 Secondary safety endpoint

The secondary safety endpoint is the occurrence of permanent discontinuation from treatment due to an adverse event. The number and percentage of subjects permanently discontinued from treatment is included in the summary of discontinuations from IMP (Section 10.2).

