## 1.2 Trial objectives, endpoints, and outcomes

Objective	Endpoint/Outcome

Primary
 
To assess the safety and tolerability of neridronic acid in subjects with CRPS.
	
Primary
 
 
• Occurrence of any treatment emergent adverse event (TEAE).
 

Secondary
 
To assess the safety and tolerability of neridronic acid in subjects with CRPS.
 
To assess the efficacy of neridronic acid in treatment of CRPS.
	
Secondary
 
 
• Occurrence of permanent discontinuation from treatment due to an adverse event.
 
• Change from baseline to Week 12 and Week 26 in the current pain intensity score, using a numerical rating scale (NRS).
 
• Response to treatment, defined as at least 30% and at least 50% decrease from baseline in the current pain intensity score, at Week 12 and Week 26.
 
• Patient Global Impression of Change (PGIC) at Week 12 and Week 26.
 
• Change from baseline to Week 12 and Week 26 in the Pain Interference score of the Brief Pain Inventory (BPI).
 

---

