## 10.2 Subject discontinuations

Discontinuations from the trial and from IMP will be presented for allocated subjects overall, and per country.

Reasons for discontinuations from the trial and from IMP will be presented for:

- Subjects allocated and discontinued from the trial
- Subjects allocated and discontinued IMP intake.
- Subjects allocated and discontinued from the trial per trial phase, i.e., during the treatment period, and during the follow-up period

Percentage denominator will be the number of subjects discontinuing.

The details for “other reasons” will be presented in a listing, if applicable.

If more than 10% of the allocated subjects discontinue the trial/IMP the distribution of the time to discontinuation from trial/IMP will be summarized using time-to-event methods. Time will be days until discontinuation. The time to discontinuation from the trial will be censored at the subject’s last planned visit, i.e., Visit 11. The time to discontinuation from IMP will be censored at the last planned infusion visit (Visit 5) or at the early termination visit in case of premature discontinuation from the trial, whichever occurs first.

All data will be presented in a subject data listing sorted by site.

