### 15.1 Adverse events

All adverse events with start date/time after first IMP administration in a subject administered a trial treatment will be defined as treatment emergent adverse events (TEAE) irrespective of causal relationship.

A pre-treatment non-TEAEs is an adverse event starting in the pre-treatment period as defined in Section 8.2.2.

If there are partial dates or times, an adverse event will be considered treatment emergent unless the information available will clearly exclude it. Further details can be found in Section 20.1.6.1.

The causal relationship of TEAEs to IMP is categorized as follows:

Category	Assessment by investigator:
Related	certain probable/likely possible
Not related	unlikely not related
Unknown	unassessable/unclassifiable conditional/unclassified causal relationship is missing

A TEAE is considered to be ‘expected’ when the nature or intensity is consistent with the information in the neridronic acid investigator’s brochure. Otherwise, it is considered to be an ‘unexpected’ TEAE. Expectedness will be assessed by the sponsor.

The following overview tables will be generated overall, i.e., for the single treatment group neridronic acid 400 mg.

1. Summary of the number and percentage of subjects with at least 1:

- TEAE.
- Serious TEAE.
- Non-serious TEAE.
- Unexpected TEAE.
- Related TEAE.
- Related serious TEAEs.
- TEAE leading to discontinuation from IMP.
- TEAE leading to discontinuation from the trial.
- Deaths.

The percentage denominator will be the number of subjects.

2. Summary presenting the number of TEAEs per subject categorized as 0, 1, 2, 3, 4, 5, and >5.
3. Summary of the number and percentage of TEAEs for:
  - TEAEs.
  - Serious TEAEs.
  - Non-serious TEAEs.
  - Unexpected TEAE.
  - Related TEAEs.
  - Related serious TEAEs.
  - TEAE leading to discontinuation from IMP.
  - TEAE leading to discontinuation from the trial.

The percentage denominator will be the total number of TEAEs.

If more than 10 subjects discontinue the trial/IMP due to TEAE, the incidence and the incidence rate of TEAEs leading to discontinuation from the trial/from IMP will be summarized by SOC and PT.

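### SAP 15.6 takes the only secondary safety endpoint, permanent treatment discontinuation due to an adverse event, from the Section 10.2 disposition summary instead of the Safety Set table in 15.1

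*SAP*

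**What the plan says.** Protocol 1.2 lists one safety item among the secondary endpoints: "Occurrence of permanent discontinuation from treatment due to an adverse event". The first sentence of SAP 15.6 repeats that definition. The second sentence says where the result will be found: "The number and percentage of subjects permanently discontinued from treatment is included in the summary of discontinuations from IMP (Section 10.2").

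SAP 10.2 opens with "Discontinuations from the trial and from IMP will be presented for allocated subjects overall, and per country". It then plans tables of reasons for stopping the trial or the IMP and states "Percentage denominator will be the number of subjects discontinuing".

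Two passages assign the analysis set differently. SAP Table 1 puts the secondary safety endpoint on the Safety Set and discontinuations on the Allocated Set. SAP 15 (unless otherwise specified) and protocol 1.5.3 both place safety analyses on the Safety Set.

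SAP 15.1 plans, without any threshold condition, an overview of subjects with at least one event of several kinds. One row is "TEAE leading to discontinuation from IMP", and for that overview "The percentage denominator will be the number of subjects". SAP 15.5 sends the primary endpoint to this same overview: "The incidence and incidence rate for any TEAE is included in the summary of the number and percentage of subjects with TEAE (Section 15.1").

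**The concern.** The endpoint asks what proportion of treated subjects had to stop the drug for good because of an adverse event. The sentence that designates its result loses the cause and points to a disposition table with a different population and percentage base.

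A programmer or report author who follows 15.6 could label either of two wrong figures as the secondary safety result:

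- **All-cause IMP discontinuation.** This mixes in stops for withdrawal of consent, protocol deviations and other reasons.
- **The adverse-event share of those who stopped.** This describes the mix of reasons, not a risk. It can stay constant while the risk rises several-fold, or move because other reasons become more or less common.

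In a single-arm trial whose purpose is to describe safety, the designated safety results should be per-subject risks on the set the plan names.

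**Working it through.** The documents give no expected discontinuation rate and no calculation for this endpoint, so there is no planned figure to reproduce. The check compares the passages and then illustrates the size.

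**Step 1. What each place would yield**

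| Place | Numerator | Denominator | Population |
|---|---|---|---|
| Endpoint (protocol 1.2, SAP 15.6 first sentence, SAP Table 1) | permanent IMP stop due to an adverse event | all subjects in the set | Safety Set |
| SAP 15.6 second sentence, read literally | permanent IMP stop, any cause | not stated | as in 10.2 |
| SAP 10.2, reasons | IMP stop by reason | subjects discontinuing | Allocated Set |
| SAP 10.1, IMP row | IMP stop, any cause | allocated subjects | Allocated Set |
| SAP 15.1 overview row | subjects with a TEAE leading to IMP discontinuation | number of subjects | Safety Set |

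Only the 15.1 row has the cause, the denominator and the population of the endpoint. SAP 10.1 does not fill the gap. Its general IMP row is all-cause, and its only cause-specific row is for deterioration in renal function, which the protocol lists as other data and not as an endpoint.

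**Step 2. Size of the difference**

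Inputs: N = 290, the planned size (protocol 1.5.1, SAP 5.2). The stop counts are assumed. Allocated and treated numbers are taken as equal, and adverse event is assumed to be one of the recorded reasons, because the CRF page is not in the documents.

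With *a* adverse-event stops and *d* stops in all, the three figures are *a*/*d* (10.2 reasons), *d*/290 (all-cause) and *a*/290 (endpoint).

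| *a* of *d* | *a*/*d* | *d*/290 | *a*/290 |
|---|---|---|---|
| 4 of 6 | 66.7% | 2.1% | 1.4% |
| 10 of 15 | 66.7% | 5.2% | 3.4% |
| 20 of 30 | 66.7% | 10.3% | 6.9% |

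From first row to last the risk rises by 20/4 = 5 times, while the 10.2 share does not move.

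Holding the total at 15 stops and varying the mix:

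- 5 adverse-event stops: 5/15 = 33.3% against 5/290 = 1.7%
- 9 adverse-event stops: 9/15 = 60.0% against 9/290 = 3.1%
- 12 adverse-event stops: 12/15 = 80.0% against 12/290 = 4.1%

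The all-cause rate is 15/290 = 5.2% in all three cases, so it is blind to the mix.

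**Step 3. Effect of the analysis set alone**

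If 285 of 290 allocated subjects were treated, 10 adverse-event stops give 10/285 = 3.5% against 10/290 = 3.4%. The set mismatch contradicts Table 1 but hardly changes the number. The distortion comes from the discontinuer denominator and the all-cause numerator.

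**Step 4. How closely the 15.1 row matches the endpoint**

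It differs in two words. It does not say permanent, although the treatment-discontinuation definition in SAP 8.2.2 and the listing of adverse events leading to discontinuation in 15.1.1 both do. It also counts TEAEs, which 15.1 defines through "All adverse events with start date/time after first IMP administration", while the endpoint says adverse event.

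**The case against.** The strongest reply is that 15.6 defines the endpoint correctly in its first sentence, Table 1 assigns it to the Safety Set, and the second sentence only says where output can be found. Section 10.2 tabulates reasons, so the adverse-event count is very probably there. The discontinuer denominator may be meant only for the reasons, with the overall percentage taken on allocated subjects as in 10.1. All of this is fair. It shows that the numerator is likely recoverable, but on neither reading does 10.2 state the percentage the endpoint needs.

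A second reply concerns the remedy. SAP 20.1.2.1 takes discontinuation reasons from the End-of-Trial and Treatment Completer pages, whereas adverse-event records carry their own field for action taken with the IMP (protocol 12.3.1). The SAP does not say which source feeds the 15.1 row, so the two counts could differ, and one could instead keep the 10.2 count and divide it by the Safety Set. This stands as a reason to name the source in the reworded sentence. It does not rescue the present text, because the right definition is the same with either source.

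A third reply is that the label differences are small. Protocol 12.3.1 records a pre-treatment event that worsens on or after dosing as a new event, so the gap between adverse event and TEAE is confined to a non-worsening pre-treatment event that leads to a stop. The action-taken categories also separate interruption from withdrawal. That is right, and it makes the label change a tidy-up.

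Finally, the counts above are hypothetical, the trial is exploratory with no inferential testing, and the 15.1 percentage will be produced anyway. These points limit the severity.

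**Conclusion.** The concern holds, as a minor point. SAP 15.6 designates the wrong table, and with it the wrong numerator or denominator, for the only secondary safety endpoint; this conflicts with the endpoint's own definition and with the Safety Set assignment in Table 1, SAP 15 and protocol 1.5.3. No other passage repairs the designation. It is not a missing analysis, since a Safety Set row of the right kind is already planned in 15.1.

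Under the assumed counts the designated figure could read 66.7% whether the risk is 1.4% or 6.9%, or 5.2% all-cause where the risk is 3.4%. The sizes rest on those counts, on N = 290, and on adverse event being a recorded reason for stopping. The mismatch in the text does not depend on any of them.

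**What to change.** 1. **Reword the second sentence of SAP 15.6.** State the result as the number of Safety Set subjects who permanently stopped the IMP because of an adverse event, divided by all Safety Set subjects. Refer to the subject-level overview in 15.1, as 15.5 does for the primary endpoint.
2. **Name the numerator source in that sentence.** Say whether the cause comes from the recorded reason for stopping the IMP or from the action-taken field of the adverse-event record, and which prevails if they disagree.
3. **Align the 15.1 row label.** Add the word permanent, and either state that an adverse event leading to IMP discontinuation means a TEAE or count all adverse events in Safety Set subjects.
4. **Keep the discontinuer denominator in 10.2** for the distribution of reasons only.

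The cost is one reworded sentence and one row label, with no new data, table or analysis.
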